**Table I – First/Initial session i.e. First Visit**

Visit 2/3/4 – Prior Session/Mid-point Session/Control Session	Duration (mins)
Baseline End-tidal CO 2 (EtCO 2 ) is measured.	<1
Devices: Gyrostim Rotating Chair and Joystick	60-70

Prior Session:  MAXIMUM number of sets: 10  Each set duration: 6-7 mins
	

During each set:

1. GVR will be turned on at **R MA**.
2. The chair will be rotated with an acceleration of 10 deg/s/s to a constant velocity up to 120 deg/sec.
3. Head movements will be cued every 10 seconds, alternating between pitch forward (chin resting to chest) and pitch backward (head upright). There will be a total of 9 forward and 9 backward movements (3 mins).
4. Motion perception (Coriolis illusion) will be measured using the joystick.
5. The chair and GVR will be paused for 2 minutes.
6. Motion sickness questionnaire score (Pensacola diagnostic criteria and Oman's subjective magnitude estimation score 0-20) will be recorded.

#### ***Midpoint Session:***

MAXIMUM number of sets: 10

Each set duration: 6-7 mins

During each set:

1. For first **four** sets, GVR will not be turned on. From fifth to maximum set, GVR will be turned on at **R MA**.
2. The chair will be rotated with an acceleration of 10 deg/s/s to a constant velocity up to 120 deg/sec.
3. Head movements will be cued every 10 seconds, alternating between pitch forward (chin resting to chest) and pitch backward (head upright). There will be a total of 9 forward and 9 backward movements (3 mins).
4. Motion perception (Coriolis illusion) will be measured using the joystick.
5. The chair and GVR will be paused for 2 minutes.
6. Motion sickness questionnaire responses (Pensacola diagnostic criteria and Oman's subjective magnitude estimation score 0-20) will be recorded.

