Our first specific aim is to evaluate the effect of timing and magnitude on the administration of our nonpharmaceutical treatment to motion sickness. While we have previously demonstrated that our approach can mitigate motion sickness if introduced prior to the provocative stimuli, one of the goals of this study is to determine the efficacy if we administer the treatment following the onset of symptoms. Validating the efficacy following symptom onset would alleviate the need for certifying the device to be worn within the landing suit and greatly enhance flexibility to implement this treatment during recovery operations. Our first hypothesis is that efficacy of galvanic vestibular reduction to reduce motion sickness severity will depend on the timing and magnitude of the administration. We will test this hypothesis by exposing subjects to provocative Coriolis crosscoupling stimuli on a rotating chair using a repeated measures counter-balanced design to compare motion sickness severity across three treatment interventions: prior to stimulus (symptom) onset, following symptom onset, and placebo control. The GVR amplitude will be customized based on individual sensitivity. Symptom severity will be assessed using both subjective reports and objective autonomic measures (electrogastrography and cardiac interbeat intervals). We expect that the most effective administration will be GVR delivered prior to the onset of symptoms, but that it will continue to be more effective relative to placebo control even if delivered following symptom onset.

Our second specific aim is to evaluate the effect of GVR amplitude on functional fitness task performance. One disadvantage of pharmaceutical approaches is that increased drug dosage is often accompanied by sedative side

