movements will be cued every 10 sec, alternating between pitch forward (chin resting on chest) and pitch backward (head upright). This timing allows for subjects to use the joystick to record motion perception associated with each pitch forward and backward movement. There will be a short pause following each set of 9 forward/backward movements (3 min) to review symptoms with the subject, although motion sickness symptoms will be obtained throughout the test protocol using verbal reports. Subject will continue making head movements until the motion sickness endpoint (moderate nausea) or the maximum number of paired forward/backward head movements (90) has been reached.

**Galvanic Vestibular Reduction (GVR) application:** We will use a repeated measures design to compare motion sickness severity for each subject across the three treatment interventions: prior to stimulus onset, following symptom onset, and placebo control. For each session, the participant will be instrumented for GVR prior to rotation. The amplitude (up to 2.5 mA) will be customized based on individual sensitivity (see below). The order of the three sessions will be counter-balanced across subjects. For the “*prior to*” session, the GVR will be initiated just prior to the chair motion. For the “*midpoint*” session, the GVR will be initiated following 4 of 10 sets of movements or the onset of slight nausea, whichever occurs first. For the “*control*” session, the subject will be instrumented without turning on the GVR throughout the testing.

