**Motion sickness recordings:** Objective measures of sickness will be obtained using electrogastrography (EGG) methodology that we've employed successfully in previous motion sickness studies (Cevette et al. 2014a) (IRB # 18-005564, 14-003906). The EGG measurements will require seated baseline reading for approximately 20 mins prior to rotation. We propose up to three alternate methods for subjective reporting (to be finalized during pilot testing). First, an acute score will be derived using the Pensacola diagnostic criteria introduced by Graybiel et al. (1968). Using this scale, the subjective intensity of eight different modalities of symptoms and signs are reported on a “slight/moderate/severe” basis, and then numerically to arrive at a weighted “malaise index”. We will also obtain a subjective magnitude estimation score using a scale 0-20, with 20 indicating vomiting (Oman et al. 1986). And finally, participants will be asked to quantify motion sickness severity along multiple dimensions (e.g., gastrointestinal, central, and peripheral symptoms, Gianaros et al. 2001) using a multi-point scale for each.

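### The midpoint session has two conflicting GVR start rules; under Table II's fixed rule with the moderate-nausea stop, anyone who stops within four sets receives no GVR

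*Combined protocol and SAP*

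**What the plan says.** All references are to the combined protocol and SAP.

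- **Aim.** Under Research Question and Aims, the first specific aim states that "one of the goals of this study is to determine the efficacy if we administer the treatment following the onset of symptoms".
- **Start rule, narrative.** In Study Design and Methods, the paragraph on GVR application says that in the midpoint session "the GVR will be initiated following 4 of 10 sets of movements or the onset of slight nausea, whichever occurs first".
- **Start rule, table.** Table II, Midpoint Session, step 1 says that for the first four "sets, GVR will not be turned on. From fifth to maximum set, GVR will be turned on at" the individual amplitude R. It mentions no symptoms.
- **Stop rule.** The motion sickness test paradigm paragraph says "Subject will continue making head movements until the motion sickness endpoint (moderate nausea"), or until "the maximum number of paired forward/backward head movements (90) has been reached". The Data Analysis Plan also treats test duration as ending at moderate nausea. Table II gives ten sets as a maximum but does not repeat the nausea stop.
- **Control.** The participant is instrumented and GVR stays off throughout.
- **Analysis.** The Data Analysis Plan compares three conditions by repeated measures ANOVA and labels the middle one as treatment following symptom onset. The opening Protocol paragraph calls it only a midpoint administration.

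**The concern.** The two start rules agree for anyone who reaches the end of set 4 without slight nausea. They differ only for participants who become nauseated earlier, and these are the clearest cases of treatment after onset. Efficacy after onset is both a stated goal and part of the combined deliverable.

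The text introducing the two visit tables presents them as the full method, so an operator could reasonably run sessions from Table II alone. Another operator could follow the narrative. Early responders would then receive different treatments under one label, and exposure missed during a session cannot be restored in the analysis.

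There is also a smaller labelling issue, which arises under either rule. A participant with no symptoms at the end of set 4 starts GVR before onset, although the analysis plan describes the condition as post-onset. The trigger is nausea alone, whereas on the Pensacola scale "the subjective intensity of eight different modalities of symptoms and signs are reported", so absence of nausea is not the same as absence of symptoms.

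**Working it through.** **1. The two rules side by side**

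| Participant in midpoint session | Narrative rule | Table II rule with the nausea stop |
|---|---|---|
| No slight nausea by end of set 4 | GVR from set 5 | GVR from set 5 |
| Slight nausea in sets 1-4, no stop by end of set 4 | GVR from slight nausea | GVR from set 5 |
| Moderate nausea within sets 1-4 | GVR from slight nausea until the stop | No GVR; delivered like control |

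In the last row, the narrative rule gives some GVR provided the participant passes through slight nausea first and reports it. The protocol provides for that, since "motion sickness symptoms will be obtained throughout the test protocol using verbal reports".

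**2. Largest difference in start point**

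Inputs: 9 forward/backward pairs and 3 minutes of cued movement per set (Table II); "Each set duration: 6-7 mins"; maximum 90 pairs (10 sets x 9).

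- Pairs: 4 x 9 = 36, and 36/90 = 40%.
- Elapsed time: 4 x 6 = 24 to 4 x 7 = 28 minutes.
- Cued head movements within that time: 4 x 3 = 12 minutes. The rest is pause, spin-up and scoring.

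These are ceilings, approached only by someone nauseated almost at once who still lasts four sets.

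**3. The plan's own sample size**

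The Power Statement gives n = 16 for a standardized difference of 0.75, two-sided alpha 0.05 and 80% power. Taking 0.75 as mean difference over SD of the paired differences:

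- Normal approximation: ((1.960 + 0.842)/0.75)² = 13.95, so 14.
- Exact paired t-test (noncentral t, 15 df): power 0.801 at n = 16. The stated figure reproduces as a paired calculation.
- At the requested minimum of 30, power is 0.978; at the target accrual of 40, it is 0.996.

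The Power Statement does not say which pair of conditions it covers. Midpoint versus control is assumed here.

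**4. Illustration of dilution**

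Let q be the share who stop within four midpoint sets under Table II. The documents do not give q. Assume zero effect in that share, 0.75 in the rest, and a within-group SD of differences of 1. The mean is 0.75(1 - q) and the variance is 1 + 0.75²q(1 - q), so

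dz = 0.75(1 - q) / √(1 + 0.5625 q(1 - q)).

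Example, q = 10%: 0.675 / √1.0506 = 0.675/1.025 = 0.659.

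| q | Mean effect | dz | Power, n=16 | Power, n=30 | Power, n=40 |
|---|---|---|---|---|---|
| 0 | 0.75 | 0.75 | 0.80 | 0.98 | 0.996 |
| 5% | 0.71 | 0.70 | - | 0.96 | 0.99 |
| 10% | 0.675 | 0.66 | 0.69 | 0.94 | 0.98 |
| 20% | 0.60 | 0.575 | 0.58 | 0.86 | 0.94 |
| 30% | 0.525 | 0.50 | 0.46 | 0.75 | 0.865 |

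The powers go with the dz column, not with the mean effect. On this model, power stays at or above 80% up to q of about 26% at n=30 and 36% at n=40.

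**The case against.** **Impact is unproven.** The documents give no onset or stopping times, and excluding people with a history of severe motion sensitivity should keep early stopping down. With 30 to 40 participants, power holds up over a fair range of q. This stands. A reader might infer that the midpoint comparison is underpowered or that many sessions will be untreated; the documents support neither. If staff follow the narrative rule, the untreated share is close to zero.

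**The illustration does not measure the cost of choosing Table II.** Under the narrative rule, the same early stoppers might get GVR only shortly before stopping, and nothing in the documents says they would then gain 0.75. This also stands. A reader might take the whole loss in the table as attributable to Table II, but it only shows what untreated sessions would do under the stated assumptions.

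**The midpoint label is disclosed.** The narrative names the session midpoint and states the four-set fallback openly, so starting symptom-free participants at set 5 is a known choice. This is largely right. It would go too far to call the condition invalid as a test of post-onset treatment; how it is described in the report is what needs care.

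None of this reconciles the two start rules. Both are current operating instructions, and Table II cannot be set aside as a summary when the protocol presents the tables as the full method.

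**Conclusion.** The conflict is real and should be fixed. The two rules give different treatment to anyone with slight nausea in sets 1-4, by up to 36 of 90 movement pairs. The no-GVR consequence follows by logic, on one condition: Table II's start rule is used together with the moderate-nausea stop.

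The size of any dilution is unknown. The power figures rest on assumed q, zero effect in early stoppers, 0.75 in everyone else, and the paired reading of the plan's effect size. The case for acting does not depend on power. As written, the treatment of the earliest responders is undefined, and one of the two available readings leaves them untreated in the condition meant to test post-onset GVR.

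**What to change.** **Change Table II, Midpoint Session, step 1 to:**

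> GVR is off from the start of the session until the onset of slight nausea or the end of set 4, whichever occurs first; it is then turned on at R mA and used during rotation in all remaining sets.

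The last clause is needed because step 1 is listed as something done in each set and step 5 pauses GVR between sets. Without it, the text could be read as resetting GVR to off each time.

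**Also:**

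- Repeat the moderate-nausea stop in Table II.
- Record the set and the symptom scores at the moment GVR starts.
- Keep all participants in the main midpoint versus control comparison.
- Report how many started GVR without any symptom, and how many stopped before receiving any GVR.
- Where GVR started before symptoms, describe the comparison as midpoint administration, not as treatment after onset.

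No post-onset subset analysis is needed; the plan does not contain one.

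**Cost.** Two edits to Table II and a few more items to record and report. No visits or procedures are added, because verbal symptom reports and set-by-set scores are already planned. The downside is a slightly more modest claim about treatment after onset.

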#### ***Control Session:***

MAXIMUM number of sets: 10

Each set duration: 6-7 mins

During each set:

 
1. GVR will be not be turned.
 
2. The chair will be rotated with an acceleration of 10 deg/s/s to a constant velocity up to 120 deg/sec.
 
3. Head movements will be cued every 10 seconds, alternating between pitch forward (chin resting to chest) and pitch backward (head upright). There will be a total of 9 forward and 9 backward movements (3 mins).
 
4. Motion perception (Coriolis illusion) will be measured using the joystick.
 
5. The chair and GVR will be paused for 2 minutes.
 
6. Motion sickness questionnaire responses (Pensacola diagnostic criteria and Oman's subjective magnitude estimation score 0-20) will be recorded.
 
	
Post- EtCO 2 is measured.  Motion Sickness Questionnaire responses (gastrointestinal, central and peripheral symptoms on VAS: 0-10) will be recorded after the end of session.	2

**Table II – Next three sessions (Prior, Mid-point, and Control Sessions)**

### Subject Information

*Target accrual is the proposed total number of subjects to be included in this study at Mayo Clinic. A “Subject” may include medical records, images, or specimens generated at Mayo Clinic and/or received from external sources.*

Target accrual: 40 participants

Subject population (children, adults, groups): Healthy adults with normal vestibular function

Inclusion Criteria: For our purposes, participants must be able to consent to participate themselves and be 21 to 55 years of age and must be able to attend in-person sessions at the Mayo Aerospace Medicine and Vestibular Research Laboratory in Scottsdale, AZ. No racial/ethnic groups will be excluded, although all participants must be fluent speakers of English.

Exclusion Criteria: History of vestibular disease, migraine, or significant balance disorder; traumatic brain injury, recent middle ear infection or recent motion sickness (within 72 hrs), history of severe motion sensitivity, women who are pregnant.

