Most non-pharmaceutical approaches to motion sickness mitigation involve some type of training. Cowings et al (2018) recently demonstrated improvement with autogenic feedback training, although subjects in this study were required to undergo a 2 hr refresher training prior to each provocative test. Vestibular habituation or desensitization training has been very effective in aviation, generally relying on the desensitization to one provocative motion transferring to the operational environment (Cheung and Hofer 2005). Although the success rate ranges between 50-85%, the retention of this training in the absence of exposure has not been clearly established beyond a few months (Samuel and Tal 2015). The Russian cosmonauts rely on a systematic preflight desensitization training program (Bryanov et al. 1975; Matsnev et al. 1983). While the effectiveness of this program for inflight mitigation may result in reduced symptoms early inflight, the incidence and severity of motion sickness cosmonauts experienced during our field tests clearly suggest that retention through spaceflights of six-month duration is not effective in mitigating post-landing symptoms. Several authors have noted that one consequence of the cosmonaut desensitization program is an alteration of vestibular reflexes that may be dysfunctional for operational tasking (Wetzig et al. 1993; Clement et al. 2007).

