**Protocol:**

Participants will attend four sessions of the experiment on four separate days. The first/initial session will be required to establish galvanic vestibular sensitivity measures to customize the GVR level, and to characterize performance on a sensorimotor-cognitive test battery as a function of GVR stimulus level. In the next three sessions, we will test the efficacy of GVR to mitigate motion sickness by comparing conditions across three separate counterbalanced sessions: administration from the onset of testing, at a midpoint of testing, and placebo control. Each session will be conducted on four separate days at least two days apart so that there is no influence on each other. Using a repeated measures design, we will compare motion sickness symptom onset, severity and recovery during standardized motion sickness testing using a rotatory chair.

**Equipment:** The motion sickness experiments will be conducted using our GyroStim Multi-Axis Rotating Chair (used in the previous IRB approved project – IRB # 19-003257) located in Aerospace Medicine and Vestibular Research Lab at Mayo Clinic Arizona (Figure 1A). Subjects will be restrained in a chair but free to bend their head forward to elicit Coriolis cross-coupling stimuli. Subjects will be tested with their eyes closed. Galvanic

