
 
• An obstacle (foam block 30 cm height) will be positioned between the chair and the 4m turning point, and the patient will be required to step over this obstacle twice, once on the way toward the turning point and again on the return back.
 
• The time stops when the patient is seated.
 
	

Cognitive Performance  Device: Oculo-Cognitive Addition Test (OCAT):  0mA (baseline), 1.75mA (GVR)
	5

Galvanic Vestibular Sensitivity:  Device: Gyrostim Rotating Chair and Joystick  The chair will be rotated for up to 60 seconds with an acceleration of 10 deg/s/s to a constant velocity up to 120 deg/sec and deceleration of 10 deg/s/s to a complete stop.  5 trials of rotations will be tested for each GVR amplitudes:  0mA (baseline), 1.25mA, 1.5mA, 1.75mA and 2mA  The GVR will be turned on before each corresponding rotation.  1 minute washout period after each rotation.  Motion perception (i.e., yaw) will be measured using the joystick for each rotation.  Decide the lowest GVR amplitude that reduced motion perception, say R mA.
	20

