#### Data Analysis Plan:

We hypothesize that efficacy of galvanic vestibular reduction to reduce motion sickness severity will depend on the timing of the administration, being more effective when administered prior to stimulus (symptom) onset. For specific aim 1 we will use repeated measures ANOVA to examine changes in symptom severity, test duration (terminated at moderate nausea), and recovery to baseline across three levels: prior to stimulus (symptom) onset, following symptom onset, and placebo control. For specific aim 2 we hypothesize that functional task performance will decline with increasing levels of galvanic vestibular reduction amplitude. We will use repeated measures ANOVA to examine changes in cognitive performance, dynamic posturography, and dual tracking performance across up to 5 levels of GVR amplitude. Sample size estimates are based on: (1) the expected variability ( $s^2$ ) in the response parameters, (2) the alpha ( $\alpha$ , type I) error level, or probability of incorrectly concluding there is an effect when responses are equivalent, (3) the magnitude of the effects to be detected between the means ( $\mu_1, \mu_2$ ), and (4) the certainty (statistical power,  $1 - \beta$ ) with which the effect is to be detected. Sample sizes can be calculated based on the expected standardized differences ( $\Delta$ ) between conditions (Fisher and Van Belle 1993).

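### The 72-hour motion sickness exclusion at entry does not agree with a two-day minimum gap between sessions that themselves provoke sickness, and the aim 1 analysis has no term for the resulting carryover

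*Combined protocol and SAP*

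**What the plan says.** Subject Information, Exclusion Criteria, lists "recent middle ear infection or recent motion sickness (within 72 hrs), history of severe motion sensitivity, women who are pregnant". It does not say whether the 72-hour item is checked only at enrolment or again later, or whether sickness caused by the trial counts.

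The Protocol section sets the spacing: "Each session will be conducted on four separate days at least two days apart so that there is no influence on each other". No reason is given for that spacing.

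The three sessions after the first are the efficacy sessions: "In the next three sessions, we will test the efficacy of GVR to mitigate motion sickness by comparing conditions across three separate counterbalanced sessions". In each one, the motion sickness test paradigm gives the stopping rule, quoted here up to its last word: "Subject will continue making head movements until the motion sickness endpoint (moderate nausea) or the maximum number of paired forward/backward head movements (90) has been". The GVR application paragraph adds: "The order of the three sessions will be counter-balanced across subjects".

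The Data Analysis Plan states: "For specific aim 1 we will use repeated measures ANOVA to examine changes in symptom severity, test duration (terminated at moderate nausea), and recovery to". The rest of that sentence completes the third outcome, a return to baseline, and lists the three conditions to be compared. It names no period, sequence or carryover term.

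Table II lists only an end-tidal CO2 reading before rotation at Visits 2 to 4. Symptom scores come within each set and after the session. The motion sickness recordings paragraph adds a seated electrogastrography baseline of about 20 minutes, which is not a symptom score.

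**The concern.** The plan uses two intervals for what looks like the same question: how long after a bout of motion sickness a person is fit to be tested. At entry it is 72 hours. Between sessions designed to cause sickness it can be about 48 hours. Nothing in the documents explains the difference or exempts trial-induced sickness.

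At stake is the within-subject comparison on which aim 1 rests. If a session leaves an after-effect, the next session is measured on a shifted baseline. Counterbalancing evens out a simple period effect, but not an after-effect whose size depends on the condition that came before. A Prior session can follow only Midpoint or Control, and a Control session can follow only Prior or Midpoint, so the two inherit different after-effects on average. The planned model has no term that would show this. With no symptom score tabled before rotation, residual symptoms at the start of a visit would not be seen in the scores either.

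**Working it through.** **The plan's own sample size.** The Power Statement gives 16 subjects for a standardized difference of 0.75, two-sided alpha 0.05 and 80% power. For a paired t-test the exact power is 0.771 at n = 15 and 0.801 at n = 16, so 16 is reproduced. The present point does not change that figure.

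**Intervals.** Inputs are the 72-hour window (Subject Information) and the two-day minimum (Protocol), read as start to start.

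- Minimum gap: 2 × 24 = 48 hours.
- Shortfall against the window: 72 - 48 = 24 hours.
- Efficacy sessions that follow another efficacy session: the second and third, so 2 of 3 can start inside the window. If the window and the gap agreed, the count would be 0 of 3.

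**Carryover under counterbalancing.** Let P, M and C be the true mean severities for Prior, Midpoint and Control. Assume that all six orders are used equally and that a session adds L times its own true severity to the next one. Each condition is then first in 2 of 6 orders and directly follows each other condition in 2 of 6.

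- Mean observed Prior: P + L(M + C)/3.
- Mean observed Control: C + L(P + M)/3.
- Difference: (P - C) + L(C - P)/3 = (P - C)(1 - L/3).

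By symmetry the same factor applies to Midpoint minus Control. Positive L stands for residual sickness, negative L for habituation. The documents give no value for L. The last three columns take the design difference of 0.75 and leave the standardizing SD unchanged.

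| L (assumed) | Factor 1 - L/3 | 0.75 becomes | Paired-t power, n = 16 | Paired-t power, n = 30 |
|---|---|---|---|---|
| 0 | 1.00 | 0.75 | 0.80 | 0.98 |
| 0.1 | 0.97 | 0.725 | 0.77 | 0.97 |
| 0.2 | 0.93 | 0.70 | 0.74 | 0.96 |
| 0.3 | 0.90 | 0.675 | 0.71 | 0.95 |
| -0.2 | 1.07 | 0.80 | not shown: apparent gain is bias | not shown |

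In this model a true difference of zero stays zero. The carryover rescales a real difference and does not create one.

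**Dependence on the orders used.** The plan does not say which orders make up the counterbalancing. The requested 30 divides evenly by six, but the target accrual of 40 does not (40 = 6 × 6 + 4). With an uneven split, or with only some of the orders, the factor would differ from 1 - L/3.

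**The case against.** **No criterion is broken.** A reader might infer that participants tested at 48 hours fail the plan's eligibility rule. The documents do not support this. The 72-hour item is a subject exclusion, and nothing makes it a condition of each session or extends it to trial-induced symptoms. Two days is also a floor, and a participant who finishes a session without symptoms is not in the window. If two days apart meant two clear days in between, the gap would be about 72 hours and the mismatch would largely close. All of this stands. What remains is that the plan does not say which reading it intends or why the shorter interval is enough.

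**The direction of bias is not established.** It is tempting to conclude that residual sickness dilutes the GVR benefit. That needs L to be positive. If exposure makes people less susceptible, and sicker sessions do so more, L is negative and the benefit is inflated. This objection stands.

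**The Background does not contradict the spacing.** It says "the retention of this training in the absence of exposure has not been clearly established beyond a few months", and a reader might set this against the two-day gap. The sentence concerns habituation or desensitization training programmes, not the after-effect of one provocative session. It gives the claim of independence no support, but it does not refute it.

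**Checking at entry is not misplaced.** Visit 1 has no sickness test, but it rotates participants at up to 120 deg/sec and measures their motion perception to choose the GVR amplitude. A check before that visit is reasonable. The open question is what applies afterwards.

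**The carryover model is crude and its effect modest.** Sessions stop at moderate nausea, so participants who reach that endpoint under two conditions leave with similar final severity, and carryover would differ less than the model implies. Test duration runs the other way, since longer is better, so the formula does not transfer to it directly. At 30 complete subjects, power stays at 0.95 or above for L up to 0.3. These limits stand. They argue for treating the factor as illustrative, not for leaving carryover out of the analysis.

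**Conclusion.** The point holds as an internal inconsistency combined with a gap in the analysis. At the permitted minimum spacing, up to two of three efficacy sessions can begin 24 hours inside the window used at entry, reading two days as 48 hours. The statement that sessions do not influence each other has no support in the documents, and the aim 1 model could neither detect nor adjust for an influence if there were one.

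The size of any bias is unknown. Under equal use of six orders and first-order carryover proportional to severity, the Prior-minus-Control difference is scaled by 0.97 to 0.90 (L = 0.1 to 0.3) or by 1.07 (L = -0.2). L is an assumption throughout. The main cost is an after-effect that cannot be separated from the treatment comparison; loss of power is secondary. This review takes no position on which interval is right.

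**What to change.** 1. The study team should reconcile the exclusion criterion in Subject Information with the spacing rule in the Protocol section, so that the recent-sickness window and the minimum gap between sickness sessions agree. They should also state whether the criterion applies before Visits 2 to 4 and whether trial-induced episodes count.
2. Record the actual time since the previous session, and a symptom score before rotation, at each of Visits 2 to 4.
3. Specify the set of orders used, include period in the aim 1 model, and add a sensitivity analysis with the preceding condition as a term.
4. Remove the statement that the present spacing leaves no influence between sessions.

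The cost is a short amendment, a brief symptom rating at three visits and possibly slightly longer scheduling. In the model, period uses 3 - 1 = 2 degrees of freedom, and the sensitivity analysis a few more. No extra participants are needed.
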